## 9.2 Statistical analysis for the primary outcome measure in the parallel cluster study

Analyses will follow CONSORT guidelines (Schulz et al. 2010, Piaggio et al. 2012). A flowchart will describe the inclusion and follow-up of participants by study arm and by implementation block. Baseline characteristics and outcomes will be described by study arm and by implementation block using summary statistics such as median and interquartile range or number and percentage.

We will test for significant difference in the primary outcome of antibiotic prescription between study arms by comparing proportions and their 95% confidence intervals (CI). Primary analysis of superiority will be performed according to the intention-to-treat (ITT) principle (Committee for Proprietary Medicinal Products, 2001), with sensitivity analyses exploring differences between ITT, per-protocol and complete cases analysis approaches. The results will be stratified by sex, age group (young infants ages 1 to 59 days, children aged 2 months to 5 years, and children aged 5 to 14 years), and select clinical variables (respiratory symptoms, fever without clinical source, gastrointestinal complaints, skin problems, ear and throat problems, anemia, and malnutrition).

We will also use multi-level logistic regression with HF, patient ID, and time included as random effects (Kahan et al. 2012) to explore the effect of demographic and clinical variables on the outcome of interest. Effect modification by sex, age group, and the same clinical variables will be assessed by incorporating an interaction between arm and the respective variable, acknowledging that power will be low.

Primary analysis will be performed on initial consultations only (i.e. first visit for a particular illness episode), allowing multiple observations per patient over the course of Phase 1, but only one observation per illness. We will apply a 14-day period from the initial visit, during which no second initial visit will be possible and all subsequent visits will be marked as re-attendance by default. In the secondary sub-analyses, re-attendance visits between day 0 and day 7 will be considered, as well as longitudinal analyses of the complete visit history per patient. Further details on the primary and secondary analyses will be provided in the statistical analysis plan.

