3.3 Sample size

The primary analysis will evaluate whether the use of ePOCT+ for case management of sick children in PHC facilities results in decreased antibiotic prescriptions (superiority analysis) at the initial consultation. Superiority in antibiotic prescription is defined as a relative decrease of $\geq 25\%$ in the proportion of children prescribed an antibiotic. We estimated a cluster size of 660 patients (monthly utilization of 220 – accounting for up to 30% non-adherence and/or loss to follow-up from 315 – over 3 months) and an intraclass correlation coefficient of 0.025. Non-adherence here is defined as HWs not using the application for all eligible patients that come to the HF for various reasons. To have 80% power to detect a 25% reduction in antibiotic prescription (from 35% to 26%), for a two-sided hypothesis test at alpha of

0.05, we would require a minimum of 11 clusters per arm. With 16 clusters per arm, over 3 months, we expect a total of 10,500 children in each study arm. Considering the pragmatic/adaptive nature of the study design, if a higher antibiotic prescription in the control arm is encountered (e.g. 45% or higher), each cluster study of 5-6 health facilities per study arm will be sufficiently powered to show a statistically significant reduction in the primary outcome. Sample size calculations were performed in R statistical software (version 4.0.3) using the CRTSize package (Rotondi, 2015).

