6.1 Analysis methods

Analyses will follow CONSORT guidelines (Campbell, Piaggio, Elbourne, & Altman, 2012; Piaggio et al., 2012; Schulz, Altman, & Moher, 2010; Zwarenstein et al., 2008). Outcomes will be described by arm using summary statistics. Baseline characteristics will be compared by study arm and by cluster study to ensure that the pragmatic allocation of health facilities and sequential rollout of the study did not introduce significant bias. Baseline characteristics which will differ between treatment arms within and over all clusters will be described using summary statistics.

Since the documentation of final treatment in both arms is part of the per protocol definition, only the PP population can be used for primary outcome analysis. The primary outcome will be evaluated using a random effects logistic regression model with the binary outcome variable of antibiotic prescription, with study arm and covariates at patient-level (e.g. age, sex) as fixed effects, and cluster (health facility) and patient included as random effects. Binary secondary outcomes will be evaluated in the same way. All estimates will be reported as odds ratios (ORs) with two-sided 95% confidence intervals (CI). The study will be deemed a success if antibiotic prescription at the initial consultation is 25% less in the ePOCT+ arm compared to the control arm, although we expect a greater reduction based on limited pilot data.

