Effect modification of the primary outcome of antibiotic prescription will be performed in groups of patients where the highest reduction in antibiotic prescription is expected, and areas of extension of the content of the algorithm compared to the version tested in the previous ePOCT study. Effect modification by sex, age group (young infants ages 1 to 59 days, children aged 2 months to 5 years, and children aged 5 to 14 years), respiratory symptoms, fever without clinical source, gastrointestinal complaints (vomiting and diarrhea), skin problems, ear, nose and throat problems, will be assessed by incorporating an interaction term between the treatment arm and the respective variable, acknowledging that power will be low. Furthermore in order to adjust for potential imbalances in baseline characteristics between study groups, relevant baseline characteristics will be included as fixed effect variables in the final model. Baseline characteristic imbalance will be determined by statistical method (i.e., comparisons of treatment arms over all clusters and within clusters) and by consensus among the study analysis team.

The number of children lost to follow up may be quite high due to the difficult nature of phone follow-up at day 7, as found in previous studies with day 7 phone call lost to follow up rates of 13-25% (Christie et al., 2018; Hannigan, Chisale, Drew, Watson, & Gallagher, 2019; Nguhuni et al., 2017).

Comparatively, the proportion not cured at day 7 is expected to be quite low (3%). The use of a complete case analysis was therefore selected for the secondary outcome of day 7 clinical cure, as it would be the most conservative analysis. If we were to use the “enrolled set” and considered all day 7 lost to follow up as not being cured, this would dilute the difference between arms. Not considering lost to follow up cases as failures is also the approach used for similar studies with high number of LTF

and low proportion of outcomes (Källander et al., 2018). We may adjust the final model for further baseline variables (not already included as fixed effect variables) which are associated with missing outcome data (analogous to performing multiple imputation in the case of a single endpoint). As with the other fixed effect variables, baseline characteristic imbalances among patients lost to follow up will be determined by consensus among the study analysis team.

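### The effect-modification tests in SAP 6.1 leave facility-to-facility variation in the subgroup effect out of the interaction's standard error, so they are too liberal wherever such variation exists

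*SAP*

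**What the plan says.** SAP 6.1 evaluates the primary outcome with a random effects logistic regression that has arm and patient-level covariates as fixed effects, "and cluster (health facility) and patient included as random effects". Effect modification is then examined for seven variables: sex, age group in three levels, respiratory symptoms, fever without clinical source, gastrointestinal complaints, skin problems, and ear, nose and throat problems. For each one, effect modification "will be assessed by incorporating an interaction term between the treatment arm and the respective variable, acknowledging that power will be low".

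Protocol 9.2 is close to this: "We will also use multi-level logistic regression with HF, patient ID, and time included as random effects", with effect modification assessed by "incorporating an interaction between arm and the respective variable, acknowledging that power will be low". It adds time to the random part and nothing else.

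Neither document mentions a random slope, a facility-by-subgroup term, robust standard errors or a facility-level subgroup comparison. SAP 3.2 allocates whole facilities to arms, and SAP 3.3 gives the scale: "With 16 clusters per arm, over 3 months, we expect a total of 10,500 children in each study arm".

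**The concern.** An arm-by-modifier interaction compares the subgroup contrast in intervention facilities with the same contrast in control facilities. Arm is a facility-level factor, so the comparison is replicated over 16 facilities per arm. A facility random intercept absorbs differences in the overall level of prescribing. It does not absorb differences between facilities in how much more often they prescribe for, say, respiratory complaints than for others. A patient random effect does not do this either. Without a slope term, the model treats each facility's contrast as the same apart from binomial noise, and judges the interaction against the number of children.

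Some variation of this kind is plausible on the SAP's own reasoning, since SAP 3.1 justifies clustering by the influence of the facility on its providers' practice. At stake is over-calling the subgroups in which ePOCT+ appears to work better or worse. The only caveat in either document concerns low power, which warns about missed effects and not about false ones.

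**Working it through.** **Inputs from the documents.** 16 facilities per arm, 660 children per facility, ICC 0.025, 35% versus 26% prescribing, two-sided alpha 0.05, 80% power (SAP 3.3).

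**Inputs assumed, because the documents do not give them.** The between-facility SD of the subgroup log odds ratio (tau), taken from 0 to 0.3; and the subgroup share q, taken as 50%, 20% and 5%. For scale, ICC 0.025 implies an intercept SD of sqrt[(0.025/0.975) × π²/3] = 0.29 on the logit scale. A tau of 0.3 therefore means that the subgroup contrast varies about as much between facilities as overall prescribing does.

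**The plan's own figure.** Comparing 35% with 26% needs 410 children per arm without clustering. The design effect is 1 + 659 × 0.025 = 17.475. Then 410 × 17.475 / 660 = 10.86, which rounds up to the SAP's 11 clusters per arm. The inputs are read correctly.

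**Interaction test without a slope.** The binomial variance of one facility's subgroup log odds ratio in an arm with rate p is 1/[660 p(1−p) q(1−q)]. For q = 0.5 this is 0.02664 at 35% and 0.03150 at 26%, with mean v = 0.02907. The model's standard error for the interaction is sqrt[(0.02664 + 0.03150)/16] = 0.060. The true variance is larger by the factor 1 + tau²/v, so

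type I error = 2 × {1 − Φ[1.96 / sqrt(1 + tau²/v)]}.

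For q = 0.5 and tau = 0.2: 1 + 0.04/0.02907 = 2.376, square root 1.541, 1.96/1.541 = 1.272, giving 20.4%. The other cells follow in the same way (v = 0.04542 at q = 0.2 and 0.15300 at q = 0.05):

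| Subgroup share | tau 0 | tau 0.1 | tau 0.2 | tau 0.3 |
|---|---|---|---|---|
| 50% | 5.0% | 9.1% | 20.4% | 33.3% |
| 20% | 5.0% | 7.6% | 15.3% | 25.6% |
| 5% | 5.0% | 5.8% | 8.1% | 12.0% |

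**Simulation check.** 2,000 trials per setting, with fixed facility effects standing in for random intercepts and no patient effect or covariates. Rejection at tau 0.1, 0.2 and 0.3 was 8.3%, 19.7% and 33.1% (50% share); 7.3%, 16.4% and 24.9% (20%); and 5.8%, 8.3% and 12.0% (5%). At tau 0 it was 4.2-5.5%. A t-test on the facility-level subgroup log odds ratios, 16 against 16, rejected in 4.0-6.1% of trials in every setting.

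**Precision with the slope included.** Adding 2 tau²/16 to the variance gives the following; the detectable ratio of odds ratios at 80% power is exp[(1.96 + 0.84) × SE].

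| Subgroup share | SE, no slope term | Detectable ratio | SE at tau 0.2 | Detectable ratio |
|---|---|---|---|---|
| 50% | 0.060 | 1.18 | 0.093 | 1.30 |
| 20% | 0.075 | 1.24 | 0.103 | 1.34 |
| 5% | 0.138 | 1.47 | 0.155 | 1.55 |

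**The case against.** The strongest reply is that the inflation rests entirely on tau, which appears in neither document. The ICC describes overall prescribing and says nothing about subgroup contrasts. At tau 0 the test is exact, and at tau 0.05 the rate is only 6.0% even for a half-and-half subgroup. The largest figures need both a high tau and an even split. Sex is the only listed modifier that is clearly near 50:50, and it is the one for which a facility prescribing habit is least convincing. This stands: the result has to be given as a conditional range.

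It can also be said that the SAP does not write out the random part of the interaction model, so intercepts only is an inference. That is true. It is the natural reading of "cluster (health facility) and patient included as random effects", however, and if slopes are intended the SAP should say so.

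Three stronger conclusions are tempting, and the documents do not support them.

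- A reader might compound the error over seven modifiers: at 20% each, 1 − 0.8⁷ = 79%, against 1 − 0.95⁷ = 30% at 5%. That needs tau near 0.2 and near-even splits for every modifier, and independence among complaint groups that may overlap. The 30% is a separate multiplicity question that a random slope does not answer.
- A reader might infer that these tests will decide later changes to the algorithm. Protocol 3.2, 4.1 and 8.2 base Phase 2 changes on trends in the collected data, expert review and retrospective analysis. No passage makes the Phase 1 interaction tests a trigger.
- A reader might think the low-power caveat is wrong and should go. For a 5% subgroup the detectable ratio of odds ratios is already 1.47 without a slope, so the caveat can be fair, and the correction makes it more apt.

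**Conclusion.** The omission is real and holds on the natural reading of both documents: between-facility variation in the subgroup effect has no place in the interaction's standard error. Its size is conditional. With 16 facilities of 660 children per arm, 35% and 26% prescribing, and tau between 0.1 and 0.3, type I error at nominal 5% is about 9-33% for a 50:50 subgroup, 8-26% for a 20% subgroup and 6-12% for a 5% subgroup. It is 5% if the contrast does not vary. None of these rates should be read as a fixed property of the plan. The mechanism is certain; tau and the subgroup shares are assumed. The tests are subgroup analyses of the primary outcome and do not enter the success criterion, which rests on overall prescribing. This is a worthwhile, inexpensive improvement and not a threat to the main result.

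**What to change.** In SAP 6.1, write out the random part of the interaction models and add a facility random slope for the modifier to each one. The three-level age group needs two slopes. Prespecify a facility-level analysis as the alternative, or as the fallback if a model does not converge: compute the subgroup log odds ratio in each facility and compare 16 with 16 facilities by t-test. Align Protocol 9.2 with this.

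Keep the statement that power will be low, and add the expected precision under the slope model for assumed subgroup shares and a range of tau, as in the second table above.

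The cost is wider interaction intervals and slightly more complex models. No new data are needed, and the primary analysis and success criterion do not change.

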3.2 Allocation of health facilities to study arms

The 32 health facilities to be included in the study will be selected from all eligible health facilities in the participating districts (Rusizi and Nyamasheke). Eligible health facilities include public health centers with at least 19 consultations with children between 2 months and 5 years of age per week. Cluster inclusion and exclusion criteria will first be applied to the full list of health facilities in the participating districts prior to selection of the 32 health facilities. Health facilities (or clusters) will be allocated (1:1), to using ePOCT+ (intervention) or routine care (control group). Due to the pragmatic nature of the study, randomization is not possible. Health facilities will be allocated first to one of the three implementation blocks using geographical considerations, and then split into study arms, also using geographical considerations. Similar sample size by study arm and by implementation group will be maintained as much as possible.

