3.4 Statistical interim analyses

Interim analyses for the primary endpoints will be performed after each of the cluster studies. As previously mentioned, minor implementation changes may be made throughout the study to adapt to issues discovered from the monitoring data and feedback from the field at the time of the interim analyses. The Principal Investigators may decide to terminate the study prematurely according to certain circumstances, such as ethical concerns that cannot be resolved, in case of safety of the participants being compromised (e.g. if the benefits no longer outweigh the risks), alterations in accepted clinical practice that make the continuation of the study unwise, or evidence of harm of the intervention. In case of premature study termination, the Rwanda National Ethics Committee will be notified as per local guidelines.

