5.4 Baseline characteristics

The baseline cluster (health facility) characteristics that will be summarized by study arm include:

- Number of health facilities by district
- Average number of patients seen per month by health facility
- Availability and readiness of basic health care services score based on the Rwandan Service Provision Assessment (median and IQR)

The baseline patient characteristics that will be summarized by study arm, and for the overall study include:

- Demographics: sex (number and percentage); age (median and IQR), age groups 0-2 months, 2 months - 5 years, 5-14 years (number and percentage)
- Medical history: Main reasons for consultation, history of fever (number and percentage)

Given the pragmatic nature of the study, and so as not to influence the normal management of patients and their outcome in the control arm, clinical signs and comorbidities will not be systematically collected in the control and intervention arm.

Baseline data will be compared across the study arms to confirm no bias due to lack of true randomization.

6. Main analyses

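### SAP 6.1 picks the primary model's further adjusters from observed imbalance although allocation is not random, a weak rule with 16 facilities per arm; the pooled model also omits implementation block

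*SAP*

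**What the plan says.** **Allocation.** SAP 3.2 rules out random assignment of facilities: "Health facilities will be allocated first to one of the three implementation blocks using geographical considerations, and then split into study arms", again by geography. (SAP 3.1 still describes a 1:1 randomization of clusters and needs to be reconciled with this.)

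**Primary model.** SAP 6.1 specifies a random-effects logistic regression "with study arm and covariates at patient-level (e.g. age, sex) as fixed effects, and cluster (health facility) and patient included as random effects". Unnamed relevant baseline characteristics are then added as fixed effects to correct imbalance: "Baseline characteristic imbalance will be determined by statistical method (i.e., comparisons of treatment arms over all clusters and within clusters) and by consensus" of the study analysis team. For the day-7 cure analysis: "We may adjust the final model for further baseline variables (not already included as fixed effect variables) which are associated with missing outcome data".

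**Role of the baseline tables.** SAP 5.4: "Baseline data will be compared across the study arms to confirm no bias due to lack of true randomization". SAP 6.1 gives a similar purpose: "to ensure that the pragmatic allocation of health facilities and sequential rollout of the study did not introduce significant bias".

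**Interim looks.** SAP 3.4: "Interim analyses for the primary endpoints will be performed after each of the cluster studies".

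**Block.** Protocol 4.1 compares the primary outcome within implementation blocks. The exploratory multi-level model in Protocol 9.2 has a random effect for time. The SAP uses the blocks for interim analyses, baseline description and exploratory trends. The model that gives the pooled primary estimate has no block or time term.

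**The concern.** In a randomised trial, adjustment mainly buys precision. Here it also has to remove confounding by geography, so the rule that selects the adjusters is part of the estimator. A rule that waits for an imbalance to be noticed has two weaknesses. With 32 facilities it will miss facility-level imbalances large enough to matter. It also leaves the planned estimate unidentified until the data are in, possibly after results by arm from earlier blocks have been seen. Asking the same baseline comparison to show that no bias arose is more than it can do.

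Block is a separate and smaller matter. Blocks differ in place and in calendar time. If prescribing differs between them, the facility random effect absorbs that difference and the standard error of the arm contrast is larger than it need be.

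**Working it through.** The documents give no covariate effects, imbalances or block rates. Those inputs are assumed and varied. Simulated results come from linear models of facility proportions, a proxy for the SAP's mixed logistic model.

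**1. The plan's own figure.** Inputs from SAP 3.3: 35% vs 26%, two-sided 5%, 80% power, 660 children per facility, ICC 0.025. Two proportions need 410 children per arm. The design effect is 1 + 659 × 0.025 = 17.475. Then 410 × 17.475 / 660 = 10.86, rounded up to 11 facilities per arm, as stated. The between-facility SD used below follows from the same inputs: √(0.025 × 0.35 × 0.65) = 0.075.

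**2. How often an imbalance is noticed.** For a two-sample t-test of 16 vs 16 facilities (30 df) and a true imbalance of 0.5 SD, the noncentrality is 0.5 × √(16/2) = 1.41. It is flagged 27.8% of the time at the 5% level, 39.8% at 10% and 54.9% at 20%.

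**3. What is left if the test alone decides.** The bias from one imbalanced covariate is correlation × facility SD × imbalance. At a correlation of 0.3 this is 0.3 × 0.075 × 0.5 = 0.011, or 1.1 percentage points. The simulation has three independent facility covariates, one of them imbalanced by 0.5 SD, and a true effect of 35% to 26.25%. The last two columns give power when the imbalance runs against ePOCT+.

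| Correlation (assumed) | Unadjusted bias, points | Bias left after 5% selection, points | Power, 5% selection | Power, fixed list |
|---|---|---|---|---|
| 0.2 | 0.72 | 0.35 | 82% | 85% |
| 0.3 | 1.1 | 0.55 | 81% | 90% |
| 0.4 | 1.54 | 0.76 | 80% | 96% |

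The fixed list removes the bias. Less than 72% of it survives selection because samples that escape the flag tend to have the smaller observed imbalances.

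**4. Timing.** The SAP compares arms over all clusters, which needs block 3. By then the primary endpoint has been analysed for blocks 1 and 2. The trial is open-label (SAP 3.1) and no blinding of the analysis team is stated. Knowledge of earlier results is therefore possible, but no date for the choice is given.

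**5. Block.** Assumed 5/5/6 facilities per arm and a true effect of 35% to 26.25%.

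| Control rates by block (assumed) | Power without block | Power with block |
|---|---|---|
| Equal (35% in all) | 89% | 89% |
| 30/35/40%, ICC 0.025 within block | about 85% | 90% |
| 30/35/40%, ICC 0.025 in total | 93% | 97% |
| 28/35/42%, ICC 0.025 within block | 80% | 90% |

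In the second row, rejection with no true effect is about 2.5% without block and 5% with it, so the test without block is conservative. Bias needs unequal splits. With 5/5/6 intervention and 6/5/5 control facilities at 30/35/40%, the arm means without any effect are (5×30 + 5×35 + 6×40)/16 = 35.3% and (6×30 + 5×35 + 5×40)/16 = 34.7%, a shift of about 0.6 points.

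**The case against.** The stated rule looks at baseline data, not outcomes. SAP 5.4 narrows the likely candidates, and consensus can add a variable that a test misses. The covariates named are patient-level, where about 2 × 10,500 = 21,000 children carry more information than 32 facilities, although clustering limits it. All of this stands, and it makes step 3 one reading of the rule for one kind of covariate. But SAP 6.1 neither includes nor excludes facility characteristics, and allocation by geography acts at exactly that level.

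On block, the defence is that each block is half intervention and half control, and that Protocol 4.1, the interim analyses and the baseline tables already work by block. That also stands as far as bias goes: with equal splits there is none, and power stays near 80% or above in the scenarios shown. None of these provisions enters the pooled model, though.

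Three stronger readings are tempting, and the documents do not support them.

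- *The adjusters will be chosen after seeing results, or to suit them.* Neither SAP 3.4 nor 6.1 dates the choice or ties it to outcomes. If the most favourable of eight adjustment sets were picked while a 0.5 SD imbalance favoured ePOCT+, a false significant benefit would occur 9.3% of the time, against about 2.5% with a fixed list. But a single unadjusted model already gives nearly 6% there, so much of the excess is ordinary confounding.
- *The success criterion moves with the covariates.* SAP 6.1 says "The study will be deemed a success if antibiotic prescription at the initial consultation is 25% less in the ePOCT+ arm" than in the control arm. It reports odds ratios and does not say whether this figure is read from the adjusted model or from crude percentages; Protocol 9.2 compares proportions. Crude percentages would not move.
- *Omitting block biases the result.* Only with uneven splits, as shown above.

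**Conclusion.** The concern holds, in limited form. For a comparison that is not randomised, selecting adjusters from observed imbalance is a weaker method than a list fixed in advance. It misses a 0.5 SD facility-level imbalance about 72% of the time at the 5% level. At an assumed correlation of 0.3 it leaves about half of a 1.1-point bias if the test is the only criterion. The baseline comparison can describe the arms but cannot show that bias is absent. Leaving out block is an efficiency loss that depends on the blocks differing, and including it costs almost nothing if they are alike. All magnitudes are illustrative, since they rest on assumed correlations, imbalances and block rates and on a linear facility-level proxy. Any effect on the 25% criterion applies only if that criterion is read from the adjusted model. The trial is not invalidated, but the SAP should be changed.

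**What to change.** In SAP 6.1:

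- (a) Add implementation block (three levels) as a fixed effect in the primary and secondary models.
- (b) Replace imbalance-driven selection with a list drawn from SAP 5.4, fixed before any outcome data by arm are examined, including the first interim analysis. The list: age group, sex, facility volume from pre-study data (for example the 2019 HMIS figures used for eligibility) and readiness score. Include main reason for consultation and history of fever only if both arms record them in the same way. Decide on district now, from the known allocation.
- (c) Keep imbalance-driven models for the primary outcome as sensitivity analyses.
- (d) For day-7 cure use the same list. Keep adjustment for predictors of missingness in the main model, because the SAP cites losses of 13-25% in previous studies against about 3% not cured, but name the candidate variables in advance.
- (e) Delete the purpose clause "to ensure that the pragmatic allocation of health facilities and sequential rollout of the study did not introduce significant bias". In SAP 5.4 end the sentence "Baseline data will be compared across the study arms to confirm no bias due to lack of true randomization" after the mention of study arms. Keep the tables as description.

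**Cost.** Wording, plus a few facility-level degrees of freedom. Block (2), volume, readiness and district take them from 30 to 25, and the t critical value from 2.04 to 2.06. If none of the three facility covariates predicts prescribing, power falls from about 87% to 83% (simulated with volume, readiness and district, without block), or to 81% if one is also imbalanced by 0.5 SD. With balanced covariates, power is unchanged at a correlation of 0.2 each (87% vs 87%) and higher at 0.3 (92% vs 87%).
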